## 1.11 Time points of statistical analysis

*Analysis time point of AGIL-CV as a supplement to AGIL:*

Statistical analyses for the primary research questions are planned for Months 12, 24 and 60. For the secondary research questions, previous cardiovascular results are taken into account at these analysis time points.

1 Title Page

Abbott GmbH & Co. KG

Documentation Plan AGIL (GER 08-05)

Long term Documentation of the Safety and Efficacy as well as the Effects on Quality of Life and Work Productivity in Patients with Rheumatoid Arthritis under HUMIRA® (Adalimumab) in Routine Clinical Practice (AGIL)

Product Name: HUMIRA®

Type of Study: Non-interventional Study (NIS)

Date: 28-10-2008

Principal Investigator:

Biometry

Tel
Fax

Sponsor:

Abbott GmbH & Co. KG

This study will be conducted in compliance with this protocol and other applicable regulatory and legal requirements. No use or disclosure outside Abbott is permitted without prior written authorization from Abbott.

2 Synopsis

Sponsor	Abbott GmbH & Co. KG [REDACTED]
Title	Long term Documentation of the Safety and Efficacy as well as the Effects on Quality of Life and Work Productivity in Patients with Rheumatoid Arthritis under HUMIRA® (Adalimumab) in Routine Clinical Practice
Short title	AGIL
Type of study	Non-interventional study
Product, dose, and administration form	Adalimumab (HUMIRA®): 40 mg subcutan (s.c.) every other week
Project code	GER 08-05
Indication	Moderate to severe active rheumatoid arthritis (RA) and/or severe, active and progressive RA
Study objectives	
The primary objective of the NIS is to explore the therapeutic success, measured by improvements in the following target variables (with regard to the respective baseline value):
 
• The number of missed working days• The self-assessed work ability (WPAI)• The severity of clinical symptoms (number of tender and swollen joints, CRP and ESR, respectively; total score DAS28)• The severity of functional impairment (HAQ)• The health-related quality of life (EQ-5D) 
All of the patient and disease characteristics which are documented at baseline will be evaluated for their additional impact on the target variables (therapeutic success). Particularly the impact of previous biologic therapies on clinical target variables will be evaluated.
 
The secondary objective is to document the therapeutic success by the following variables:
 
• The number of physician visits• The number and duration of hospitalization• The number of days of impairment in non-occupational activities• The duration of morning stiffness, pain, exhaustion/fatigue• The reduction of number and dose of concomitant medication• Patient's assessment of adalimumab therapy compared to previous therapies.

Target parameters for safety evaluation of adalimumab are:

- The evaluation of safety and tolerability by the documentation and analysis of serious adverse events (SAEs) and adverse events (AEs)
- Evaluation of safety and tolerability for subgroups of patients with common frequent concomitant diseases, especially diabetes type II, cardiovascular, liver, and renal insufficiencies, and related concomitant medications.

Study population	Adult patients (≥ 18 years) with moderate to severe active RA and/or severe, active and progressive RA
Study design	Single-arm, multi-center format, prospective cohort study
Treatment duration	5 years
Methodology	Disease Activity Score (DAS28), Health Assessment Questionnaire (HAQ), Health Questionnaire Short Form (EQ-5D), WPAI
Total number of patients	2500 Patients
Adverse Events	As reported by patients and diagnosed at visits
Data analysis plan	The general biometric approach consists of evaluation of changes by descriptive statistical methods, as well as of regression analysis of parameters influencing the therapeutic success and additional subgroup analysis. By forward and backward stepwise regression, those patient and disease characteristics (baseline values of all target parameters, disease duration, previous therapies, demographic and anthropometric data, health-related quality of life etc.) will be selected which show a statistically significant partial correlation with the parameters of therapeutic success at month 3 (improvements in the number of affected joints [DAS28], HAQ, number of missed working days, and WPAI). Due to the clear temporal relation between the baseline values and the treatment effects at month 3, the selected predictors can be interpreted both as causal explanation and as prognosing factors concerning therapy-modifying influencing variables (since an reactive influence of the 3-month values on the baseline values can be ruled out). Additionally, the strength of the relationship between the predictors and the parameters of therapeutic success will be determined. The impact of the variables determined by regression analysis on the therapeutic success will be illustrated by subgroup analysis. The impact of adalimumab therapy on health-related quality of life (EQ-5D), the number of physician visits and hospitalization, the days of impairment in non-occupational activities, and the subjective symptoms (morning stiffness, pain, exhaustion/fatigue) will be descriptively evaluated and additionally analyzed by between-group comparison. Two interim analyses are planned.
Planned recruitment phase	March 2009 - March 2012
Planned study duration	March 2009 – March 2018
Product manufacturer	Abbott

3 Abkürzungen und Definitionen

AE	Adverse event
AMG	Arzneimittelgesetz
BMI	Body Mass Index
CCP	Cyclic citrullinated peptide
CRF	Case Report Form
CRO	Clinical Research Organization
CRP	C-reactive protein
DAS28	Disease Activity Score 28
DMARD	Disease Modifying Anti-Rheumatic Drug
EQ-5D	EuroQol Questionnaire 5 Dimensions
ESR	Erythrocyte sedimentation rate
FAS	Full analysis set
HAQ	Health Assessment Questionnaire
Hb	Hemoglobin
MedDRA	Medical Dictionary for Regulatory Activities
NIS	Non-interventional study
RF	Rheumatoid factor
SAE	Serious adverse event
SAP	Statistical analysis plan
SDV	Source Data Verification
WPAI-GH	Work Productivity and Activity Impairment-General Health version

4 Table of Contents

1	Title Page	1
2	Synopsis.....	2
3	Abkürzungen und Definitionen	4
4	Table of Contents	5
5	Introduction.....	7
6	Rationale	9
7	Study Objectives.....	10
8	Investigational Plan	12
8.1	Selection of Study Population	12
8.2	Number of Patients to be Enrolled	12
8.3	Investigator Selection Criteria.....	12
8.4	Study Duration.....	13
8.5	Study Conduct	13
8.5.1	Schedule of Observations	13
8.5.2	Description of Activities.....	16
8.5.3	Scales and Scores	18
8.5.4	Study Medication.....	20
9	Adverse Events	21
9.1	Adverse Event Definition and Serious Adverse Event Categories	21
9.2	Severity.....	22
9.3	Relationship to Pharmaceutical Product.....	22
9.4	Serious Adverse Event Collection Period	23
9.5	Serious Adverse Event Reporting	24
9.6	Pregnancy Reporting	25
10	Ethics and Quality.....	26
11	Case Report Form.....	28
12	Data Analysis Plan	29
12.1	Sample Size Calculation.....	29

12.2	Analysis Population(s).....	29
12.3	Missing Values	29
12.4	Level of Significance.....	30
12.5	Biometric Concept.....	30
12.6	Times of Statistical Analyses	31
13	Final Report and Publications	32
14	Literature.....	33

5 Introduction

Rheumatoid arthritis (RA) is a chronic inflammatory disease of the joints that often results in progressing joint destruction and lead to substantial functional losses, impairment, and reduced quality of life. On the social level, disease-related costs (due to lack of functionality) to be paid by social security systems are increasingly gaining priority (1), (2).

An important cytokine that activates and intensifies inflammation in RA is the tumor necrosis factor α (TNF- α). Introduction of TNF- α inhibitors 10 years ago revolutionized RA treatment options and led to the development of further recombinant antibodies and fusion products, respectively, which are called biologics. Adalimumab is one of these biologics, a human monoclonal antibody against TNF- α , which has been approved in Germany for RA treatment under the trade name HUMIRA® since 2003. Adalimumab inhibits the interaction of TNF- α with its receptors and thus suppresses the biological effect of this proinflammatory cytokine. HUMIRA® is administered as a subcutaneous (sc) injection at a recommended dose of 40 mg every other week.

Several clinical trials have shown that adalimumab both reduces the clinical symptoms of RA and decelerates the structural destruction of the joints, thus significantly improving health-related quality of life.

Patients who had been included in a non-interventional long term study and had been treated with adalimumab under conditions of routine rheumatology practice had been suffering from RA for many years (mean disease duration 12 years) and showed a high disease activity (DAS28 = 5.8). These patients experienced a significant reduction in clinical signs and symptoms of RA after 24 months of adalimumab therapy (interim analysis July 2007). 20 % of patients were in clinical remission and over 40 % had improved in their physical functionality.

Unlike the previous RA documentation, this NIS will put added emphasis on data concerning work productivity and work ability as well as data concerning health-related quality of life. This will result in an according large-scale patient documentation form.

In order to improve quality, all filled questionnaires will be checked for completeness and missing data will be added by written query. A defined percentage of participating physicians will be audited. An independent CRO will perform double data entry, perform plausibility checks and statistically evaluate the data according to criteria determined in the protocol. The results will be published after finalization of the evaluation.

The planned documentation is a non-interventional study (NIS) according to § 4 section 23, point 3, Arzneimittelgesetz (AMG) and will be conducted in compliance with the recommendations of the Verband der forschenden Arzneimittelhersteller (Association of Research-based Pharmaceutical Companies).

6 Rationale

This NIS is designed to provide additional data on treatment effects of adalimumab in the long term treatment in patients with moderate to severe active RA under conditions of routine rheumatology care. In contrast to clinical trials, all patients treated in clinical routine will be included in the NIS, independent of comorbidities, concomitant medication, severity of their illness, or features such as age and gender.

Course of work productivity and work ability, the course of health-related quality of life, and changes in functionality under long term treatment with adalimumab will be documented. The numbers of patients included in the NIS allow identifying and quantifying the impact of disease and patient characteristics on the therapeutic success.

7 Study Objectives

In this NIS, a long term documentation of treatment with adalimumab in RA patients over 60 months with 8 data collection points (visits) is planned. The documentation will be performed by the physician as well as by patient's self-assessment.

The primary objective is to explore the therapeutic success by interim analyses after 12 and 24 months of treatment as well as by the final analysis after 60 months of treatment. Improvements concerning the following target variables will be evaluated (with regard to the respective baseline value):

- the number of missed working days
- the self-assessed work ability (WPAI)
- the severity of clinical symptoms (number of tender and swollen joints, CRP and ESR, respectively; total score DAS28)
- Severity of functional impairment (HAQ)
- The health-related quality of life (EQ-5D)

At month 3, patient and disease characteristics will be evaluated with regard to their additional impact on changes in the number of affected joints (DAS28), in the HAQ, and in the WPAI. The impact on the number of missed working days will be evaluated at month 6.

The secondary objective is to document the therapeutic success by interim analyses at month 12 and 24 months as well as by the final analysis after 60 months. The therapeutic success will be evaluated by the following variables:

- The number of physician visits
- The number and duration of hospitalizations
- The number of days of impairment in non-occupational activities
- The duration of morning stiffness, pain, exhaustion/fatigue

- The reduction of number and dose of concomitant medication
- Patient's assessment of adalimumab therapy compared to previous therapies

Target parameters for safety evaluation of adalimumab are:

- The evaluation of safety and tolerability by the documentation and analysis of serious adverse events (SAEs) and adverse events (AEs).
- Evaluation of safety and tolerability for subgroups of patients with common frequent concomitant diseases, especially diabetes type II, cardiovascular, liver, and renal insufficiencies, and related concomitant medications.

8 Investigational Plan

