12.5 Biometric Concept

The general biometric approach consists of the realization of the analyses described in section 7 “Study Objectives”. The analysis principally uses descriptive statistical methods, supported by regression statistical methods and subgroup analysis.

By forward and backward stepwise regression, those patient and disease characteristics (baseline values of all target parameters, disease duration, previous therapies, demographic and anthropometric data, health-related quality of life etc.) will be selected which show a statistically significant partial correlation with the parameters of therapeutic success at month 3 (improvements in the number of affected joints [DAS28], HAQ, number of missed working days, and WPAI). Due to the clear temporal relation between the baseline values and the treatment effects at month 3, the selected predictors can be interpreted both as causal explanation and as prognosing factors concerning therapy-modifying influencing variables (since an reactive influence of the 3-month values on the baseline values can be ruled out). Additionally, the strength of the relationship between the predictors and the parameters of therapeutic success will be determined.

The impact of the features determined by regression analysis on the therapeutic success will be illustrated by subgroup analysis. Subgrouping will be done according to content-related considerations: Regarding disease activity, patients will be classified into groups with high or low DAS28 values (lower and higher 5.1 units, respectively). Regarding age, patients will be classified into groups with high or low age (lower and higher 40 years, respectively).

The impact of adalimumab therapy on health-related quality of life (EQ-5D), the number of physician visits and hospitalizations, the days of impairment in non-occupational activities, and the subjective symptoms (morning stiffness, pain, exhaustion/fatigue) will be descriptively evaluated and additionally analyzed by between-group comparison.

The tolerability analysis will be based on MedDRA coded AEs and SAEs. Incidence rates will be reported on the “Preferred Term” and “System Organ Class” levels for all patients as well as for subgroups of patients with different degrees of disease activity as well as with different previous and concomitant therapies and diseases.

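### The synopsis singles out the impact of previous biologic therapies, but Section 12.5 commits to no effect estimate or interval for it unless stepwise regression happens to select it

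*Combined protocol and SAP*

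**What the plan says.** Section 2 (Synopsis, Study objectives) first says that all baseline patient and disease characteristics will be evaluated for their impact on the target variables. It then picks out one: "Particularly the impact of previous biologic therapies on clinical target variables will be evaluated". No other predictor receives this emphasis. Section 7 does not repeat the sentence.

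Section 12.5 describes the efficacy method, and the synopsis repeats it in its data analysis entry. The candidate list reads "characteristics (baseline values of all target parameters, disease duration, previous therapies, demographic and anthropometric data, health-related quality of life etc". From this list, those characteristics "will be selected which show a statistically significant partial correlation with the parameters of therapeutic success at month 3". The plan adds that "the strength of the relationship between the predictors and the parameters of therapeutic success will be determined". On display, it says: "The impact of the features determined by regression analysis on the therapeutic success will be illustrated by subgroup analysis".

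Two efficacy splits are then defined. By disease activity, "patients will be classified into groups with high or low DAS28 values", cut at 5.1; by age, "patients will be classified into groups with high or low age", cut at 40 years. Previous therapy appears as a subgroup only in the tolerability analysis, where AE and SAE incidence is reported by disease activity "as well as with different previous and concomitant therapies and diseases".

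Section 8.5.2 records previous biologics at baseline, by drug and separately from DMARDs and glucocorticoids. Section 8.1 admits patients previously treated with other biologics. The data for the question will therefore exist.

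**The concern.** A question that the synopsis names in advance should end in an estimate with an interval, whatever the result. Under Section 12.5 the commitment to quantify appears to depend on significance. If previous therapy is not selected, a reader could take its absence as evidence of no impact, with no interval to show which effects the data exclude. The risk is greater because Section 12.5 allows selected predictors to be interpreted causally, which gives the selection step more weight than a screening step can bear.

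Two further gaps follow from the wording. Biologics are not separated from other previous therapies in the candidate list. The selection is also tied to Month 3, whereas Section 7 assesses the primary objective at Months 12, 24 and 60 and the synopsis sentence has no time limit.

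The issue is a missing commitment to an estimate. It is distinct from the familiar bias in effects that do survive selection.

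**Working it through.** **Textual check.** Is an efficacy estimate for previous biologics guaranteed anywhere?

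- Stepwise regression (Section 12.5): a generic candidate, retained if significant. No estimate is promised for unselected candidates.
- Strength of relationship (Section 12.5): promised for the predictors, which in context most naturally means the selected ones.
- Subgroup illustration (Section 12.5): covers features found by the regression. The two defined splits are DAS28 and age.
- Between-group comparison (Section 12.5): covers EQ-5D, physician visits, hospitalizations, days of impairment and subjective symptoms. It names no groups and does not include DAS28, joint counts or HAQ.
- Tolerability subgroups (Section 12.5): include previous therapies, but only for AEs and SAEs.
- Amendment I, Section 1.10: its regressions concern the cardiovascular and metabolic parameters.

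None of these guarantees the estimate.

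**Scale.** The plan states no figure to reproduce.

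Inputs from the documents: about 2500 patients (Section 8.2) and two-sided 0.05 (Section 12.4), taken here as the selection threshold because no other is given. Assumed inputs: 30% pretreated, SD of DAS28 change 1.4, and 1250 evaluable patients as a lower case. The efficacy set will be somewhat below 2500, since Section 12.2 excludes patients previously treated with adalimumab.

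SE of the difference = SD × √(1/n₁ + 1/n₀). A true difference of 1.96 × SE is selected about half the time.

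- N = 2500 (750 and 1750): SE = 1.4 × √(1/750 + 1/1750) = 0.061; 1.96 × SE = 0.12 points.
- N = 1250 (375 and 875): SE = 1.4 × √(1/375 + 1/875) = 0.086; 1.96 × SE = 0.17 points.
- If correlation with other covariates doubles the variance (also assumed), multiply by √2 = 1.41: 0.17 and 0.24 points.
- No true effect: unselected with probability 1 − 0.05 = 95%.

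**Range over the assumed pretreated share (10% to 40%), N = 2500, two-sample normal power:**

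| True difference | In points at SD 1.4 | Chance not selected |
|---|---|---|
| 0.10 SD | 0.14 | 31% to 68% |
| 0.20 SD | 0.28 | 0.2% to 15% |

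A simulation of backward elimination at the 0.05 level (10 candidates, latent correlation 0.3, 400 runs per setting) gave similar results at N = 2500 for a 20% to 30% share: 43% to 47% dropped at 0.10 SD and 2% to 3% at 0.20 SD.

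**What a fixed term would deliver.** The unadjusted 95% CI half-width is 1.96 × √(1/n₁ + 1/n₀) in SD units. For shares from 40% down to 10% it is 0.08 to 0.13 SD at N = 2500, or 0.11 to 0.18 points at SD 1.4. With the roughly 800 patients that Section 12.6 expects at Months 12 and 24, it is 0.14 to 0.23 SD, or 0.20 to 0.32 points. Correlated covariates would widen these.

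**The case against.** The strongest reply is that Section 12.5 describes only a general approach, that Section 12 defers all detail to a separate statistical analysis plan to be approved before the first interim analysis, and that the study is openly exploratory. The deferral limits what can be said about the final report. It does not fill the gap, because nothing commits that plan to this analysis and the method already stated is significance-gated. The exploratory label excuses unadjusted p-values (Section 12.4), but not leaving a named question without an estimate.

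A reader might infer more than the documents support:

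- *That the report will contain no estimate if the variable is not selected.* Section 12.5 does not say so. It is silent on unselected variables, and although the word predictors most likely means selected ones, that is an interpretation.
- *That subgroups by previous biologics are ruled out.* Section 12.5 also says that subgrouping follows substantive considerations and sets the DAS28 and age splits without a stated condition on selection. Previous biologics is simply not among the named splits.
- *That the answer turns on which correlated variable enters first.* The plan uses forward and backward techniques, and backward elimination starts from the full set, so entry order is not decisive there. Collinearity still matters.
- *That non-selection will be reported as no impact.* No passage says this; it is a risk of misreading.

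The size is also modest at full enrolment, where a difference of 0.20 SD or more would usually be selected. DAS28 and HAQ are separate outcomes, so a complete absence of estimates needs non-selection for each.

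**Conclusion.** The point holds as a gap between objective and analysis: the synopsis gives previous biologic therapy special weight, and Section 12.5 commits to no effect estimate or interval for it if it is not selected at Month 3. The gap matters mainly for small or null effects. On the assumed 30% share and SD of 1.4, differences of about 0.12 points (N = 2500) to 0.17 points (N = 1250) would be missed about half the time, and a null effect about 95% of the time. These figures illustrate scale only; the textual finding does not depend on them. A null result is also where an interval is most needed, and the cohort is large enough to give a usefully narrow one. Whether the separate statistical analysis plan closes the gap cannot be judged from these documents.

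**What to change.** In Section 12.5:

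1. Separate previous biologic exposure from other previous therapies, for example none, one, or two or more, derived from the baseline item in Section 8.5.2.
2. Include it as a fixed term in the models for change in DAS28, joint counts and HAQ, with a pre-specified adjustment set that does not depend on stepwise selection, for example baseline value of the outcome, age, sex and disease duration. Forcing in the exposure term while its adjusters are still chosen by the data would leave an interval that ignores that selection.
3. Report the adjusted difference with its 95% CI whatever the p-value, at Month 3 and at the Month 12, 24 and 60 analyses, and tabulate the outcomes by exposure group.
4. Keep stepwise selection, if wanted, as a separate exploratory analysis of the other candidates.

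The cost is a short addition to Section 12.5, carried into the separate statistical analysis plan, and a few additional models: three outcomes at four time points make 12, or 16 if tender and swollen joint counts are modelled separately. No new data are needed. The result remains an observational association and should be described as one.

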12.1 Sample Size Calculation

The primary parameter of this documentation is work productivity, which is captured by the number of missed working days. The sample size calculation is based on the results of an interim analysis of a documentation of adalimumab in RA with 4640 patients, of whom 1417 patients had been employed part time or full time. The mean number of missed working days was 26 days (standard deviation of 55 days) during the last 12 month prior to adalimumab therapy. The correlation between baseline and follow-up report is estimated with $r = 0.5$. According to these numbers, 850 employed patients are required to detect a mean difference of 5 days within 12 months at the 0.05 significance level (two-sided) with a power of 0.80. Since 30 % of patients are employed, a total number of about 2500 employed and non-employed patients are required in order to detect the specified difference in missed working days.

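### Section 6 gives an unqualified assurance on predictor effects that the sample size does not cover; for missed working days, 850 patients give 80% power only for between-group differences of about 9 to 11 days

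*Combined protocol and SAP*

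**What the plan says.** The Rationale (Section 6 of the combined protocol and SAP) makes a general statement: "The numbers of patients included in the NIS allow identifying and quantifying the impact of disease and patient characteristics on the therapeutic success". It names no outcome, effect size or power.

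Section 12.1 holds the only sample size in the main AGIL plan. It identifies the outcome: "The primary parameter of this documentation is work productivity, which is captured by the number of missed working days". Its inputs are "The mean number of missed working days was 26 days (standard deviation of 55 days) during the last 12 month prior to adalimumab therapy" and a correlation, "The correlation between baseline and follow-up report is estimated with" r = 0.5. Its result is "850 employed patients are required to detect a mean difference of 5 days within 12 months at the 0.05 significance level (two-sided"). The calculation is set at 80% power. The study is single-arm (Section 8.5.1) and the calculation uses a baseline to follow-up correlation, so the 5 days is a mean change within patients.

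The predictor analysis is a separate one. Section 12.5 uses forward and backward stepwise regression to pick the characteristics "which show a statistically significant partial correlation with the parameters of therapeutic success", and missed working days is among the outcomes. Section 12.5 places these outcomes at Month 3. For missed working days Section 7 says: "The impact on the number of missed working days will be evaluated at month 6". Table 2 collects that item at Month 6 but not at Month 3, with a six-month recall period.

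**The concern.** A mean change in the whole sample and a difference in change between two kinds of patient are different quantities. In a sample of fixed size, the standard error of a difference between two equal halves is twice that of the overall mean. A sample size for the first therefore gives no assurance about the second, yet Section 6 gives that assurance without limiting it by outcome.

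The gap falls on the outcome that sizes the study. Missed working days exist only for employed patients, so the total of about 2500 does not help. Section 12.5 keeps or drops characteristics by a significance rule. It then determines the strength of the relationship for the predictors, without saying that characteristics left out will be reported. A reader who trusts Section 6 could take a characteristic's absence from the final model as evidence that it has no bearing on missed working days. The design cannot support that conclusion for moderate effects.

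**Working it through.** **Inputs, all from Section 12.1:** SD 55 days, r = 0.5, difference 5 days, two-sided alpha 0.05, power 0.80, n = 850 employed, 30% employed, about 2500 in total. The group shares below are assumptions; the plan gives none. z(0.975) + z(0.80) = 1.960 + 0.842 = 2.802.

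**1. The plan's own figure.**
- SD of change = 55 × √(2 × (1 − 0.5)) = 55.
- n = (55 × 2.802 / 5)² ≈ 950, not 850.
- Power at 850 = Φ(5 × √850 / 55 − 1.960) = Φ(0.690) = 75.5%.
- 30% of 2500 is 750, which gives 70.2%.
- Standard variants do not give 850 either: one-sided paired 749; baseline-adjusted SD, two-sided 713.

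**2. Between-group difference detectable with 80% power.**
- SE = SD × √(1/(np) + 1/(n(1 − p))), where p is the share of patients with the characteristic.
- SD is 55 for change scores, or 55 × √(1 − 0.25) = 47.6 after adjustment for baseline.
- Even split, n = 850: SE = 3.77 or 3.27, against 55/√850 = 1.89 for the overall mean change.
- Detectable difference = 2.802 × SE.

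| Split | n = 850, change score | n = 850, baseline-adjusted | n = 750, change score | n = 750, baseline-adjusted |
|---|---|---|---|---|
| 50:50 | 10.6 | 9.2 | 11.3 | 9.8 |
| 30:70 | 11.5 | 10.0 | 12.3 | 10.6 |
| 20:80 | 13.2 | 11.4 | 14.1 | 12.2 |
| 10:90 | 17.6 | 15.3 | 18.8 | 16.2 |

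(Days per 12 months.) At an even split with n = 850, this is 35% to 41% of the 26-day baseline mean.

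**3. The same on the partial-correlation scale.** The smallest r with 80% power is tanh(2.802/√(n − 3)). That is 0.096 at n = 850 (about 0.9% of variance) and 0.056 at n = 2500.

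**4. Illustration with an assumed 5-day between-group difference.** Power = Φ(5/SE − 1.960).
- Even split, n = 850: Φ(1.325 − 1.960) = 26%; baseline-adjusted, Φ(1.530 − 1.960) = 33%.
- 20:80 split: 18% and 23%.
- n = 750, even split: 24% and 30%.
- A 5-day difference between equal halves is r = 0.5 × 5/55 = 0.045, or 0.5 × 5/47.6 = 0.052, about half of what 850 patients can detect.

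**5. Month 6.** The inputs above are 12-month figures. Suppose 6-month counts are used, the assumed difference is halved to 2.5 days, r stays at 0.5 and the split is even.
- Independent half-years: SD = 55/√2 = 38.9 and SE = 2.67 or 2.31. Power is 15.5% or 19.1%, counting both tails.
- Perfectly correlated half-years: SD and difference halve together, so power stays at 26% or 33%.

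**The case against.** The strongest reply is that the plan promises nothing the numbers contradict. A reader might infer that 80% power was claimed for the predictor analysis and that only 26% to 33% is delivered. The documents do not support that. Section 12.1 attaches 0.80 to the mean change alone, Section 6 states no power, and no section names a 5-day gap between patient groups as a target. The 26% to 33% rests on an assumed effect, an even split and 12-month inputs. The lower end also omits baseline, which Section 12.5 lists among the candidates, so the adjusted figure is the more relevant one. A partial correlation of about 0.10 is a small effect to be able to detect. All of this stands, and the power figures serve only as an illustration.

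A reader might also infer that Section 6 is wrong altogether. It is not shown to be. For outcomes recorded in all patients, about 2500 can detect partial correlations near 0.06 before losses, so the sentence is plausible there. Nor is Section 12.1 the only sample size in the document set: the AGIL-CV amendment has its own, for blood pressure, but that does not cover this regression.

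Section 12.4 calls the analyses exploratory, and Section 12 leaves detail to a separate SAP. No section says that non-selection will be read as no effect. That lowers the severity. But Section 12.4 uses the exploratory label to justify unadjusted p-values and does not qualify Section 6, and nothing in Section 12.5 guards against the misreading.

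**Conclusion.** The concern holds in limited form, as a minor point. The Section 6 assurance has no calculation behind it. For missed working days it should be qualified: on the plan's inputs, 850 employed patients give 80% power for a between-group difference in change of 9.2 to 10.6 days per 12 months at an even split. That is about twice the 5-day mean change on which the study is sized. The figure rises to 15 to 18 days at a 10:90 split, and is somewhat larger throughout with 750 employed patients. Non-selection under Section 12.5 is therefore uninformative about smaller effects on this outcome.

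This assumes SD 55 and r = 0.5 at follow-up, no losses, a two-group characteristic uncorrelated with the other candidates, and a normal approximation for what is evidently a skewed count (SD more than twice the mean). The Month 6 version needs an assumption about how half-years correlate, which the documents do not supply.

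**What to change.** - **Section 12.5.** For missed working days, list the candidate characteristics in advance. Report the estimate and 95% confidence interval for each from one model containing all of them, including the baseline value, whether or not stepwise selection retains it. State that non-selection is not evidence of no impact. This is the change that alters what can be concluded.
- **Section 6.** Limit the sentence to outcomes recorded in all patients: DAS28, HAQ, EQ-5D and the WPAI activity-impairment score.
- **Section 12.1.** State that the calculation covers only the mean within-patient change, and add the detectable between-group difference: about 9 to 11 days per 12 months at an even split, more for uneven splits. Do not repeat that 850 gives 80% power. The stated inputs give about 950, and 850 gives about 75.5%.

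The cost is wording in three sections and one extra table, with no further patients or data. The stated capability of the study becomes less favourable, and intervals from the full model will be wider where candidates are correlated.
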